## 2 STUDY OBJECTIVES AND RELATED ENDPOINTS

DS-group refers to the dose-stable group, i.e. participants receiving NR 1000 mg daily for 3 months. DE-group refers to the dose-escalation group, i.e. participants receiving NR 1000 mg in an escalating dose with 1000 mg from baseline to week 4, 2000 mg from week 4 to week 8 and 3000 mg from week 8 to week 12. PL-group refers to the placebo group.

Objective	Endpoint	
Primary	To compare the effect of orally administered nicotinamide riboside (NR), escalated to 1500 mg twice per day (3000 mg/day) in the dose-escalation group (DE-group) - versus stable dosing of 500 mg twice per day (1000 mg/day) in the dose-stable group (DS-group) on cerebral NAD-levels, at week 12.	Change in cerebral NAD/ATP- $\alpha$ ratio measured by $^{31}$ Phosphorus magnetic resonance spectroscopy ( $^{31}$ P-MRS) in the posterior brain (encompassing the occipital, parietooccipital and posterior parts of the temporal cortex).
Secondary	To assess the dose-response relationship between NR dose (1000 mg, 2000 mg, 3000 mg per day) and changes in cerebral NAD levels from baseline to weeks 4, 8 and 12.	Change in cerebral NAD/ATP- $\alpha$ ratio measured by $^{31}$ Phosphorus magnetic resonance spectroscopy ( $^{31}$ P-MRS) in the posterior brain (encompassing the occipital, parietooccipital and posterior parts of the temporal cortex).
	To compare the effectiveness of orally administered nicotinamide riboside (NR) 1500 mg twice per day versus 500 mg twice per day in augmenting the NAD-metabolome in the central nervous system (CNS) at week 12.	Change in the cerebrospinal fluid (CSF) levels of NAD or other metabolites of the NAD metabolome*, measured by LC-MS.
Exploratory	Neuroimaging	
	To compare the effect of orally administered NR in the DE-group versus DS-group on the NR related metabolic pattern (NRRP) expression at week 12.	Change in NRRP expression, measured by FDG-PET.
	To assess the dose-response relationship between NR dose (1000 mg, 2000 mg, 3000 mg per day) and changes in NRRP expression from baseline to weeks 4, 8 and 12.	Change in NRRP expression, measured by FDG-PET.
	To compare the effect of orally administered NR DE-group versus DS-group on the PD-related pattern (PDRP) expression at week 12.	Change in PDRP expression, measured by FDG-PET.

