#### Specifications (details in section)

1. Medical history includes: family history of neurological illness (what and who), family history of PD (what and who), smoking history (period, pack-years), first PD symptoms, months since first PD symptoms, occurrence and duration of REM sleep disorder symptoms, occurrence and duration of loss of smell.
2. Heart and lung auscultation, abdominal palpation, any other examination dictated by patient's condition/symptoms
3. Blood pressure, pulse, temperature
4. DAT-Scan or 18F-FDOPA PET must have been performed prior to the Baseline Study Visit.
5. CRP, ALAT, ASAT, GT, bilirubin, ALP, creatinine, urea, RBC, Hb, WBC with differential, platelets, CK, FT4, TSH, B12, folic acid, homocysteine, methylmalonic acid, sodium, potassium, glucose. Women of childbearing potential will also have a pregnancy test performed.
6. EDTA blood, snap-frozen EDTA blood, platelets, serum (see lab manual for details).
7. To ensure correct dosages during dose escalation and if necessary to resupply.

8. The patient must be on a stable dopaminergic treatment regimen. When the patient is on a stable dopaminergic treatment, the screening is over, and the patient can be included in the study. The dopaminergic treatments are listed in section 5.4. There should not be more than 3 months from the last screening to the baseline visit.
9. Record of concomitant medication: in addition to all drugs used by the patient, the type of dopaminergic medication used and the time points in the day at which each dose is taken must be registered.

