#### **Screening checklist:**

1. Patient signs informed consent for N-DOSE
2. Patient signs informed consent for consent for storage and analysis of biological material (“Samtykke for lagring av biologisk materiale i biobank for demens og aldring”)
3. Physical examination (general neurological examination) at first screening
4. MDS clinical diagnosis Criteria
5. Record current use of medication. Advise to stop any use of vit B3 supplements
6. Introduce/adjust dopaminergic treatment as described in section 5.4.
7. If the patient is ready for enrollment, they are referred to baseline study visit (including MRI and PET).
8. The patient is given the 3-day dietary registration form along with instructions on how to fill it out and deliver to the study nurse at baseline.
9. Register when the patient takes their dopaminergic medication (dose and time of the day).
10. Patient is asked to note the time of dopaminergic therapy intake on the morning of each visit
11. Visits should be planned so that the patient is at the Department at a time permitting the MDS-UPDRS to be conducted within **no less than 15min and no more than 2 hours** after the last intake of dopaminergic medication.
12. MDS-UPDRS must be conducted at the same interval from the last dopaminergic therapy dose on every visit (+/- 30min)

### 6.2.2 Baseline/Week 0

1. Investigator verifies the informed consent for the study.

2. Investigator verifies anamnestic information gathered at screening, current use of medication and medical history.
3. Investigator verifies fulfillment of inclusion and exclusion criteria.
4. The study identification number is assigned (see section 5.9).
5. Study medication is dispensed to the subject by the study nurse and the patient is reminded to take the study medication every day including the morning of each visit.
6. Register the time the patient took dopaminergic medication on the morning of the visit as well as the type and dose of the medication.
7. The following clinical examination are performed by the study nurse or investigator (see flowchart in section 6.1):
  - o Vital signs
  - o Body weight and BMI
  - o MDS CDC
  - o MDS-UPDRS: section 1&2 by study nurse/investigator, section 3&4 by investigator
  - o MDS-NMS
  - o MoCA
  - o EQ-5L
  - o GIDS-PD
8. Routine blood tests are done (see flowchart in section 6.1)
9. Samples for biobanking are taken (see flowchart in section 6.1):
  - o EDTA whole blood
  - o Snap-frozen whole blood
  - o PAXgene blood for RNA

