### 6.2.3 **During treatment (visits 2-4)**

- Should the patient need replenishing of study medication, it will be logistically handled by the study nurse.
- On visit 2 points 5-11 and 13-15 from section 6.2.2 are repeated.
- 
- On visit 3, points 5-15 from section 6.2.2 are repeated.

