## N-DOSE Protocol v3.1

The Safety Analysis Set (SAS) will include all patients having received at least one study treatment infusion after randomisation.

The Per Protocol Analysis Set (PPS) will include all randomized patients meeting the study eligibility criteria and with no major protocol deviations affecting the treatment efficacy.

The following are pre-defined major protocol deviations regarded to affect the efficacy of the intervention:

- Entering the trial when the eligibility criteria should have prevented trial entry.
- Discontinuation of intervention prior to  $84 \pm 7$  days.
- Major change in concomitant anti-Parkinson medication.
- Received or used other intervention than allocated.
- Adherence to allocated treatment below 85%.
- Visit date interval larger than  $28 \pm 7$  days between individual visits (i.e.: V1 and V2, V2 and V3 and V3 and V4)\*.
- Visit date interval larger than  $84 \pm 7$  days from V1 to V4\*.
- Not fasting before neuroimaging.

\*Due to updated findings from a pharmacokinetic study (ClinicalTrials.gov, NCT: NCT05698771, in revision) that NAD levels increase and reach a plateau within 1-2 weeks of NR treatment both in healthy individuals and persons with Parkinson's disease. A 3 week period should therefore be sufficient to assess the effects of increasing NR dosage.

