**Bergen:**

Equipment:

Scanner: Siemens Biograph mMR 3T (PET/MR)

Software: E11P

Coils: RAPID Biomedical 31P – H\_Head Coil 3T Human head V-XQ-HQ-030-01921 V01 for SIEMENS Biograph mMR 3T

To PACS: Clinical protocol

To fPACS: All sequences (entire examination)

Protocol:

Participant preparation:

The participant should fast a minimum of 6 hours before injection of 18F-FDG. A peripheral venous catheter (PVC) is then placed in the medial cubital vein. Blood glucose is measured. The required blood glucose level is below 8 mmol/L. 30 minutes before the scan 250 MBq of 18F-FDG is injected into the PVC. The participant is required to lie in a quiet, dark environment during the interval after injection and before scanning to minimize brain activity. The participants should not use mobile phones or headphones during this period. Eyes must be closed for fMRI sequences. Imaging is to be taken up to 72 hours before or after physical examination of participants.

Positioning: Localizer. Auto align if possible.

Scan parameters: Scan labelled by study ID.

MRI sequences:

- Localizer for planning of MR and PET – 1.0 min.
- 3D T1 (sagittal, 1x1x1 mm, 3D-BRAVO or MPRAGE) – 5.5 min.
- Attenuation correction map, generated using DeepMRAC – 2.0 min.
- 31P-MRS calibration: FID, multinuclear coil, generated using xnuccalc2 from NMproc-Dockers – 2 min.
- 
- 31P-MRS sequence: CSI, multinuclear coil – 15 min.

Total imaging time: 25.5 min imaging time - 35 min including changing the coil for CSI.

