## 2.4 Timing of Outcome Assessments

For all clinically planned measures, visits should occur within a window of the scheduled visit. Visits outside visit window is regarded as a protocol deviation. Visits more than 7 days outside the visit window are regarded as a major protocol deviation. The target day and visit window are defined in the protocol as:

Visit Label	Target Day	Definition (Hour window)
Screening	-90 Days	Prior to V1 (Baseline)
V1 (Baseline)	Day 0	Day 0
V2 (Week 4)	Day 28	Target day $\pm$ 72 hours
V3 (Week 8)	Day 56	Target day $\pm$ 72 hours
Last study visit* (Week 12)	Day 84	Target day $\pm$ 72 hours

\*The last study visit is defined as the visit following the last visit with randomised treatment, and where there is a study end statement.

For analysis and tabulation purposes, we define study time points as

Time Point Label	Target Day	Definition (Day window)
V1 (Baseline)	Day 0 (Randomisation)	Information up to randomisation
V2 (Week 4)	28	Days 25 to 31
V3 (Week 8)	56	Days 53 to 59
V4 (Week 12)	84	Days 81 to 87

If more than one visit fall into the same time point interval, information on all visits will be used in the analyses.

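### The 72-hour post-visit imaging allowance at V1, V2 and V3 lets a scan be taken after study drug has been started or stepped up, and the SAP would analyse a late week-4 or week-8 scan under the earlier dose

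*Protocol*

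**What the plan says.** **Imaging window.** Protocol Appendix B, participant preparation: "Imaging is to be taken up to 72 hours before or after physical examination of participants". No visit is excepted.

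**Dispensing.** Protocol 6.2.2, point 5: "Study medication is dispensed to the subject by the study nurse and the patient is reminded to take the study medication every day". Imaging is point 10 of the same list. Section 6.2.3 carries both points forward: "On visit 2 points 5-11 and 13-15 from section 6.2.2 are repeated" and "On visit 3, points 5-15 from section 6.2.2 are repeated". Specification 7 of the flow chart gives the purpose of dispensing at V1 to V3: "To ensure correct dosages during dose escalation and if necessary to resupply".

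**Dose steps.** Protocol section 2 gives the DE-group "1000 mg from baseline to week 4, 2000 mg from week 4 to week 8 and 3000 mg from week 8 to week 12", so the steps coincide with V2 and V3. Section 3.1 describes the same schedule as 30-day periods.

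**Analysis windows.** SAP 2.4 defines the baseline time point as "Information up to randomisation", V2 as days 25 to 31 and V3 as days 53 to 59.

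**Models.** The ANCOVAs (SAP 5.1.2 and 5.1.7) regress the V4 value on group and the V1 value. The mixed model (SAP 5.1.7) has group, visit and their interaction, with no term for dose.

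**Speed of response.** The footnote to the deviation list in Protocol 10.3 relies on a finding that "NAD levels increase and reach a plateau within 1-2 weeks of NR treatment".

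**The concern.** Two scan labels may not mean what the analysis takes them to mean.

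*Baseline.* A V1 scan after the first capsules is an on-drug value in both NR arms and off-drug under placebo.

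*Weeks 4 and 8.* A DE scan taken after the step is a reading at 2000 or 3000 mg filed under the visit for 1000 or 2000 mg. The dose-response objective compares 1000, 2000 and 3000 mg, and the mixed model knows dose only through visit. DE and DS both take 1000 mg up to week 4, so their true week-4 difference is zero. A late DE scan creates one.

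The major-deviation lists (Protocol 10.3, SAP 3.4.2) cover visit intervals, adherence and fasting, but not the order of scan and first new capsule. FDG-PET is acquired in the same session (Protocol 7.4), so NRRP and PDRP inherit the problem.

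**Working it through.** **Step 1. Does the text permit it?** The plan gives no figure for this, so the check begins with timing.
- Exposure in 72 h: 3 days × 2 intakes = 6 intakes, or 36 capsules. That is 3000 mg NR after V1 in either NR arm and, in DE, 6000 mg after V2 and 9000 mg after V3.
- V2 on target: day 28 + 3 = day 31, inside 25-31. V3 on target: day 56 + 3 = day 59, inside 53-59. The SAP accepts both.
- From the late edge of the visit window the scan falls on day 31 + 3 = 34 or 59 + 3 = 62, outside the SAP time-point windows.
- If the first step is put at day 30, following section 3.1, a day-31 scan is still after it.

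**Step 2. Baseline under SAP 2.4.** Appendix B permits a V1 scan after day 0, whereas SAP 2.4 stops at randomisation. If Appendix B prevails, the scan enters as an on-drug covariate. If SAP 2.4 prevails, it is not baseline and the person has no V1 value for the ANCOVA. One scan can cause one of these, not both. SAP 5.1.5 deals with a missing V4 only, so the SAP does not settle which.

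**Step 3. Size for a scan 3 days after a start or step.**

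From the documents: plateau at T = 7 to 14 days; +27% at 1000 mg and a linear rise with dose (Protocol 10.1). Assumed: cerebral NAD follows that plateau, and the shape of the rise.

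Share of the step present: f = 3/T if linear; f = 1 − 0.05^(3/T) if exponential and 95% complete at T. False week-4 DE-DS gap = 0.27f, as a fraction of baseline. Apparent change from baseline when the truth is +27%: 1.27/(1 + 0.27f) − 1.

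| Shape, T | f | False week-4 gap | Apparent change |
|---|---|---|---|
| Linear, 14 d | 0.214 | 0.058 | +20% |
| Linear, 7 d | 0.429 | 0.116 | +14% |
| Exponential, 14 d | 0.474 | 0.128 | +13% |
| Exponential, 7 d | 0.723 | 0.195 | +6% |

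**Step 4. DS-placebo ANCOVA with an on-drug baseline.** Further assumptions: SD 0.2 at both visits, V1-V4 correlation 0.5, true difference 0.27, and half the DS baseline scans taken on day 3.
- Mean shift of the DS baseline = 0.5 × 0.27f.
- Extra baseline variance in DS = 0.25 × (0.27f)², so the pooled slope is b = 0.5 × 0.04 / [0.04 + 0.125 × (0.27f)²].
- Expected estimate = 0.27 − b × 0.5 × 0.27f.

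For f = 0.214: b = 0.495, estimate 0.256. For f = 0.429: b = 0.480, estimate 0.242. For f = 0.474: b = 0.476, estimate 0.240. For f = 0.723: b = 0.447, estimate 0.226. Simulation with 20 per arm agrees to within 0.002. The range is therefore about 0.26 to 0.23 instead of 0.27.

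**Step 5. Primary contrast.** DE and DS start on the same 1000 mg, so a late V1 scan shifts both baselines alike on average and the expected adjusted DE-DS difference at week 12 is unchanged. The cost is a noisier covariate or, under the strict SAP reading, lost participants.

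**The case against.** The best case on the other side has four parts.

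1. *Intended practice looks safe.* Protocol 6.2.1 refers patients to MRI and PET when calling them for baseline, the screening checklist treats imaging as part of the baseline visit, and the flow chart puts it within each visit. Protocol 5.2 and 6.2.2 have drug taken on the morning of the visit. At V2 and V3 that dose would come from the existing supply, so a same-day scan reads the intended dose. This stands: mislabelling in practice needs a scan on a later day. But an early scan is possible, not required, and Appendix B expressly allows the later day.
2. *SAP 2.4 already protects baseline.* Only if applied strictly, and then at the price of losing the person. It gives no protection at V2 or V3.
3. *The effect may be small.* The cited plateau is not said to be cerebral, the curve shape is unknown, and 3 days is the longest permitted delay. These points are fair, which is why the linear rise is shown beside the steeper one.
4. *It is late to change conduct.* The estimated last-patient date is 22.04.2025 and the SAP is dated 16 June 2025. If those dates held, editing the imaging manual would change nothing already scanned. The analysis rules can still be changed.

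A reader might go further and infer that the primary result is biased, that on-drug baselines both distort the covariate and cost participants, or that mis-dosed scans did occur. The documents support none of these. DE and DS share the starting dose, the two baseline harms are alternatives for any one scan, and no frequency is given.

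**Conclusion.** The concern holds as a gap between the imaging window, the dispensing schedule and the SAP's time-point definitions. At V1 it can affect both NR arms; at V2 and V3 it affects the DE-group only. The exposed analyses are the dose-response mixed model, the DS-placebo ANCOVA and the FDG-PET measures. The primary DE-DS comparison is not biased in expectation.

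The sizes are illustrations for affected scans: the week-4 gap and apparent change in Step 3 describe a single scan at the 3-day limit, so the effect on a group mean scales with the proportion of such scans, which is unknown. The DS-placebo range further assumes that half the DS baselines were affected. All of them depend on cerebral NAD following the cited plateau and on the plan's own +27% and linear-dose assumptions. If no scan followed a start or step-up, there is no effect, and one sentence saying so closes the matter. The change should be made because it is cheap and bears on the trial's dose-response question.

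**What to change.** In the SAP, before unblinding:

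1. Reconcile SAP 2.4 with Appendix B. Define baseline as the last scan before the first study capsule, and state how a later V1 scan is handled.
2. Use the recorded scan and dispensing dates to flag V1, V2 and V3 scans taken after a start or a new supply. SAP 3.4.1 computes compliance from the start and end of medication per dispensation, so start dates may also be available. Set the flag from dates alone, in all arms and blind to allocation. The dose being taken at each V2 and V3 scan then follows once the arm is known.
3. Add a sensitivity run of the mixed model and the DS-placebo ANCOVA without scans taken after a start or step-up, and report their number by arm and visit. Removing flagged scans by the same date rule in every arm keeps the exclusion independent of allocation.

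The protocol passages on imaging window, dispensing and timing of the dose steps (weeks in section 2, 30-day periods in section 3.1) must be reconciled with one another. No dosing rule is proposed here.

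Cost: SAP wording, a date comparison on data that should already exist, two extra model fits, and a few scans set aside in the sensitivity run.

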### 6.2.3 **During treatment (visits 2-4)**

- Should the patient need replenishing of study medication, it will be logistically handled by the study nurse.
- On visit 2 points 5-11 and 13-15 from section 6.2.2 are repeated.
- 
- On visit 3, points 5-15 from section 6.2.2 are repeated.

### 6.2.4 ***End of study (Visit 4)***

- The patient brings with them the remaining study medication which is gathered by the study nurse for a pill count. Clinical examinations are performed as listed in section 6.1.
- Points 6-11 from section 6.2.2 are repeated.
- B-SIT is performed by either the study nurse or investigator (see flowchart in section 6.1).
- At the end of the study visit, consider changes in the dopaminergic treatment.

## 6.3 **Criteria for Patient Discontinuation**

Patients may be discontinued from study treatment and assessments at any time. Discontinuation and the reason for discontinuation (withdrawn from the study) will be registered. Specific reasons for discontinuing a patient for this study are:

- Voluntary discontinuation by the patient who is at any time free to discontinue his/her participation in the study, without prejudice to further treatment.
- Safety reasons as judged by the Principal Investigator.
- Incorrect enrolment, i.e., the patient does not meet the required inclusion/exclusion criteria for the study.
- Deterioration in the patient's condition which in the opinion of the Principal Investigator warrants study medication discontinuation (to be records as an AE or under Investigator Discretion).

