**KG5 – Determine whether NR therapy influences histone acetylation status and characterize the dose dependence of this effect.** We have recently shown that genome-wide histone hyperacetylation and altered transcriptional regulation occur in the brain of individuals with PD. Increasing neuronal NAD levels would boost the activity of the NAD-dependent histone deacetylases of the sirtuin family, potentially, ameliorating histone hyperacetylation in PD. It is currently unknown whether NR-therapy influences histone acetylation status in PD, and whether this effect is dose-dependent.

**KG6 – Confirm that NR therapy decrease neuroinflammation and characterize the dose dependence of this effect.** While it is known that NR has anti-inflammatory properties in peripheral tissues, the results of the NADPARK trial suggest it also downregulates multiple inflammatory cytokines in the central nervous system. If confirmed this would be of importance for PD and other neurodegenerative and neuroinflammatory disorders. Moreover, it is not known whether higher NR doses can induce stronger anti-inflammatory effects in PD.

**KG7 – Determine whether NR therapy alter methylation metabolism and characterize any dose dependence of such an effect.** In theory, NAD replenishment via NR administration could decrease/deplete the cellular methylation capacity. NR boosts the NAD-metabolome, leading to increased production of the degradation product nicotinamide (NAM), which is eliminated via methylation to MeNAM, Me-2-PY, and Me-4-PY, and excreted in the urine. Synthesis of Me-Nam requires the methyl-donor S-adenosylmethionine (SAM). This, in turn, could limit SAM availability for other essential methylation reactions, such as DNA and histone methylation, and neurotransmitter synthesis, including dopamine. Thus, in theory, NR would cause an increased consumption of SAM, limiting methylation reactions and generating higher levels of homocysteine. Such a phenomenon would be a particular concern for the ~60% of the population that carries MTHFR variants that reduce the efficiency of methylation. The NADPARK study showed no change in serum homocysteine levels, or any other evidence of methylation depletion associated with NR 1000 mg daily. It is, however, unknown whether such effects may occur with higher NR doses.

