### 8.1 Definitions

#### 8.1.1 Adverse Event (AE)

An AE is any untoward medical occurrence in a patient administered a pharmaceutical product and which does not necessarily have a causal relationship with this treatment.

An adverse event (AE) can therefore be any unfavorable and unintended sign (including an abnormal laboratory finding), symptom, or disease temporally associated with the use of an investigational product, whether or not related to the investigational product.

The term AE is used to include both serious and non-serious AEs.

If an abnormal laboratory value/vital sign is associated with clinical signs and symptoms, the sign/symptom should be reported as an AE and the associated laboratory result/vital sign should be considered as additional information that must be collected on the relevant CRF.

Only intensity 2 and 3 is registered as AE in eCRF, see section 8.3. An AE has to interfere with everyday life to be of intensity 2 or 3.

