### **3.4.2 Protocol Deviations**

The following are pre-defined major protocol deviations regarded to affect the efficacy of the intervention:

- Entering the trial when the eligibility criteria should have prevented trial entry.
- Discontinuation of intervention prior to  $84 \pm 7$  days.
- Major change in concomitant anti-Parkinson medication.
- Received or used other intervention than allocated.
- Adherence to allocated treatment below 85%.
- Visit date interval larger than  $28 \pm 7$  days between individual visits (i.e.: V1 and V2, V2 and V3, and V3 and V4).
- Visit date interval larger than  $84 \pm 7$  days from V1 to V4.
- Not fasting before neuroimaging.

Protocol deviations are classified prior to unblinding of treatment. The number (and percentage) of patients with major and minor protocol deviations will be summarised by treatment group with details of type of deviation provided. The patients that are included in the FAS analysis data set (see point 3.5 below) will be used as the denominator to calculate the percentages. No formal statistical testing will be undertaken.

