## **3.5 Analysis Populations**

The Full Analysis Set (FAS) will be performed using the intention to treat population, defined as all patients randomly assigned to a treatment group and attended the baseline visit.

The Safety Analysis Set will include all patients having received at least one study treatment infusion after randomisation.

The Per Protocol Analysis Set (PPS) will include all randomised patients meeting the study eligibility criteria and with no major protocol deviations affecting the treatment efficacy.

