#### 6.1.2 Sensitivity Analyses

Sensitivity analysis of data will be performed by comparing the results of analysis with the SAS and PPS populations. If there is a notable difference this will be commented upon.

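### Protocol 6.3 lets a deterioration that stops study drug be recorded outside the AE form, in conflict with 8.1.1, and the SAP's only AE sensitivity run cannot reveal the gap

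*Protocol*

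**What the plan says.** **Recording of a stop.** Protocol 6.3 states: "Discontinuation and the reason for discontinuation (withdrawn from the study) will be registered". One listed reason is a deterioration that the principal investigator considers "warrants study medication discontinuation (to be records as an AE or under Investigator Discretion". Nothing says when each route applies.

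**Definition of an AE.** Protocol 8.1.1: "An AE is any untoward medical occurrence in a patient administered a pharmaceutical product", whether or not the product caused it. It extends this to "any unfavorable and unintended sign (including an abnormal laboratory finding), symptom, or disease temporally associated with the use of an investigational product". Only intensity 2 and 3 are entered in the eCRF. Under 8.3, intensity 2 (moderate) already covers events that disturb everyday activities or need medical intervention.

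**AE analysis.** SAP 6.1.1 tabulates AEs by arm and by NR dose level, descriptively, on the Safety Set. SAP 3.5 defines that set: "The Safety Analysis Set will include all patients having received at least one study treatment infusion after randomisation". SAP 6.1.2 adds one check: "Sensitivity analysis of data will be performed by comparing the results of analysis with the SAS and PPS populations".

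**The PPS.** It excludes major deviations (SAP 3.5). SAP 3.4.2 lists among these "Discontinuation of intervention prior to" 84 ± 7 days, adherence below 85%, and a major change in anti-Parkinson medication.

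**Other outputs on stopping.** SAP 3.1 plans a CONSORT diagram with reasons for discontinuing the intervention. The status table in SAP 3.3 has no category for stopping because of an AE or deterioration. SAP 3.4.2 summarises deviations by arm with their type. No table of AEs leading to discontinuation is planned, although DAE is in the protocol's abbreviation list.

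**The concern.** A deterioration that leads to stopping study drug is an untoward occurrence on treatment, and it would normally reach intensity 2 or 3. Under 8.1.1 it belongs on the AE form. Section 6.3 offers a second route. If a site takes that route instead of the AE form, the event is missing from the SAP 6.1.1 tables, whichever analysis set is used.

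The safety objective is safety and tolerability at 1000, 2000 and 3000 mg, and the protocol's optimal biological dose is conditional on the absence of unacceptable toxicity (section 1.4, KG1). Events that end treatment are among the most informative data for both. The sensitivity run offers no protection, because it compares the AE table with a set from which most people who stopped early have been removed.

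**Working it through.** The documents state no AE rate or discontinuation rate, so there is no figure to reproduce. The check has three parts.

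**1. Effect of one unrecorded case.** Inputs: 40 participants in the DE arm and 20 each in the DS and placebo arms (Protocol 3.1 and 4.2). For *k* participants whose only AE went to Investigator Discretion, the share with an AE falls by *k*/*n*.

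- DE arm: 1/40 = 2.5 points; 2/40 = 5; 4/40 = 10.
- DS or placebo arm: 1/20 = 5 points; 2/20 = 10.

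These are maxima: a participant with another recorded AE still counts in the table.

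**2. Who leaves the PPS.** Reading the stopping deviation as before day 84 − 7 = 77, a stop on days 77 to 84 does not trigger it. The 3000 mg period, weeks 9–12 in Protocol 5.2, runs from day 57 to day 84 (28 days). The rule therefore covers 77 − 57 = 20 of those 28 days. A later stop can still leave the PPS through the adherence or medication criterion.

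**3. Whether the Safety Set versus PPS comparison could show the problem.** Assumptions, for illustration only: 12 of 40 DE participants (30%) truly have an AE; *k* of them have only a drug-stopping deterioration and stop before day 77; nobody else leaves the PPS.

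- Safety Set, all recorded: 12/40 = 30%
- Safety Set, *k* not recorded: (12 − *k*)/40
- PPS, in either case: (12 − *k*)/(40 − *k*)

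| *k* | Safety Set, recorded | Safety Set, not recorded | PPS | Gap to PPS if recorded | Gap to PPS if not recorded |
|---|---|---|---|---|---|
| 1 | 30% | 27.5% | 11/39 = 28.2% | 1.8 | 0.7 |
| 2 | 30% | 25% | 10/38 = 26.3% | 3.7 | 1.3 |
| 4 | 30% | 20% | 8/36 = 22.2% | 7.8 | 2.2 |

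Gaps are absolute differences in percentage points. The PPS figure is the same whether or not the events were recorded, because those participants are not in it. The two sets agree more closely when the events are missed than when they are recorded properly. Agreement is therefore no reassurance about tolerability.

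**The case against.** **The parenthesis may only name a reason code.** It stands in a list of reasons for discontinuation, and AE registration is required elsewhere: at every visit (Protocol 7.1) and in the CRF for all reportable events (8.4.1). No sentence says that an Investigator Discretion stop is exempt from the AE form. This reading is possible, but 6.3 does not state it; its wording offers alternatives. The objection shows that the gap may be harmless in practice. It does not remove the ambiguity.

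**The stops remain visible elsewhere.** This largely stands. CONSORT reasons, the deviation summary and the source record of date and reason (Protocol 9.1) all survive. But the reason may read only Investigator Discretion, and no output gives the dose level at stopping. MDS-UPDRS is scheduled at every visit, but Protocol 6.4.1 says withdrawn patients are not followed up. Protocol 10.4 also names the ITT set for sensitivity analyses; it cannot restore an event never entered as an AE.

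**Stronger readings that the documents do not support.** A reader might infer that the PPS removes intolerant participants from the safety result. It does not: the main AE tables use the Safety Set, which keeps them. A reader might also infer that tolerability at the higher doses is overstated. The 6.3 wording applies to every arm, investigators are blinded, and no count of such cases is given. The Rationale (KG7) does raise the possibility that greater SAM use limits reactions "such as DNA and histone methylation, and neurotransmitter synthesis, including dopamine". It does so only in theory, reports no sign of methylation depletion at 1000 mg, and leaves higher doses open. It does not say that NR worsens Parkinson's disease.

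**Conclusion.** Sections 6.3 and 8.1.1 of the protocol conflict on how a drug-stopping deterioration is recorded and must be reconciled. Taken literally, 6.3 allows such an event, in any arm, to be absent from the SAP 6.1.1 AE tables. The size is up to 2.5 points per case in the DE arm and 5 points per case in a 20-patient arm. The number of cases is unknown and may be zero. If cases were diverted, the AE share in that arm would be understated; the documents do not show that this happened, or that it would happen more at 2000 or 3000 mg.

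The PPS does not create an undercount, but the SAP 6.1.2 comparison cannot detect one and says little about tolerability. The conclusion rests on the literal reading of 6.3 and on such events normally reaching intensity 2 or 3. The 30% rate in the table is an illustration only.

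**What to change.** 1. **Protocol 6.3 and 8.1.1:** reconcile them so that a drug-stopping deterioration meeting 8.1.1 is always recorded as an AE, with Investigator Discretion kept only as a reason code. This changes how a stop is recorded, not when or why drug is stopped.
2. **Existing data:** the SAP is dated 16 June 2025 and protocol v3.1 5 June 2025, both after the estimated last-patient date of 22 April 2025. New wording alone probably comes too late to change recording at site. Check each Investigator Discretion discontinuation against source before unblinding, and enter as AEs those that meet 8.1.1. SAP 3.4.2 already classifies deviations before unblinding, so the check fits there.
3. **SAP 6.1.2:** replace the PPS comparison for AEs with a Safety Set table of discontinuations by reason, and of AEs leading to discontinuation, by arm and dose level at onset.
4. **SAP 3.5 and Protocol 10.3 (editorial):** replace infusion with at least one dose of study capsules, since the product is oral.

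The cost is one extra table, a short blinded source check and a possibly slightly higher AE count. The efficacy analyses are unaffected.
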